Scoliosis is broadly defined as deviation of the normal vertical alignment of the spinal column. Scoliosis is typically classified as congenital, neuromuscular, syndromic, or idiopathic and may be treated with observation, bracing, or surgical correction, depending on the severity and the clinical status of the patient.[1] Idiopathic scoliosis represents the most common pediatric subtype and has a prevalence of 0.5 – 5.2%, with an operative rate ranging from 3.9 – 9.8 operations per 100,000 members of the general population.[2-4] Post-operative pain following the surgical correction of pediatric scoliosis is inevitable and must be well managed to achieve the goals of patient comfort, early mobilization, and early discharge. As a result of the short- and long-term adverse effects of opioid use in the pediatric population, many practices are adopting multimodal pain management strategies to reduce the reliance on opioid analgesia.[5, 6]

Virtual reality (VR) has been extensively studied in regards to its ability to reduce peri-procedural pain and anxiety in a pediatric population.⁷ Non-pharmacological methods of distraction are a well-established method of pain control. Virtual reality, by providing a more interactive and immersive experience, has the potential to out-perform other distraction techniques. However, the specific impact of VR following scoliosis surgery has yet to be assessed.⁸ At Connecticut Children's, patients undergo multimodal pain management following scoliosis correction, including narcotics, muscle relaxants, anti-inflammatories, and gabapentin. Patients are also expected to participate with physical therapy daily. In the present study, we intend to investigate the effect of VR on subjective post-operative pain, total inpatient narcotic administration, and mobilization with physical therapy.

Research Question

Does implementation of VR reduce pain, reduce total narcotic administration, and increase mobilization with physical therapy in the immediate post-operative period following spinal deformity surgery in the pediatric population?

Primary and Secondary Aims

Primary Aim(s):

- To determine if virtual reality (VR) reduces the subjective perception of pain for pediatric patients in the acute post-operative period (until discharge) following spinal deformity surgery.

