 - Hypothesis: The mean self-reported pain level using a 10-point numeric pain scale will be a minimum of 1 point lower in patients receiving VR compared to those in the control group.

Secondary Aims:

- To determine if VR reduces the total amount of inpatient narcotic use in the acute post-operative period (until discharge) following spinal deformity surgery.
 - Hypothesis: Patients receiving VR will have reduced total inpatient narcotic administration during their hospital stay compared to those in the control group.
- To determine if VR can facilitate earlier mobilization following spinal deformity surgery.

- Hypothesis: Patients receiving VR will participate in a fewer number of physical therapy (PT) sessions prior to receiving clearance for discharge by PT staff.

Outcome Definitions/Data Points Collected

Primary Outcome:

Pain will be measured through the 10-point numeric pain scale self-reported by the patient (patient's will be between 13-18 years of age).

Secondary Outcomes:

- Mobilization will be assessed by the number of PT sessions prior to receiving clearance for discharge by PT staff.
- Patient post-operative gross motor activity level will be measured via wearable Fitbit
- Opioid utilization will be assessed by calculating the total inpatient dose of opioids administered (as documented in the EMR) during the post-operative period.
- Side effects from virtual therapy, including headaches, vertigo, and nausea

Data collected:

- Patient demographics
 - Age, Sex, Race, Language, Ethnicity
- Patient Past Medical History
- Patient medication/drug history (prescription and recreational)
- Prior experience with VR
- Surgical details
 - # of spinal levels involved in fusion
 - Duration of surgery
 - Surgical blood loss
 - Need for transfusion
 - Complications
- Radiographic imaging
- 10-point numeric pain scale ratingsPhysical Therapy notes
 - Number of sessions prior to discharge clearance, timing of sessions, duration of each session, comments from each session,
- EPIC Medication History
- Length of stay
- Timing and duration of virtual reality sessions
- Side effects from virtual therapy sessions
 - Seizures
 - Loss of awareness
 - Headaches
 - Vertigo
 - Nausea
 - Eye strain / blurred or double vision
 - Eye or muscle twitching

- Involuntary movements
- Dizziness and lightheadedness
- Disorientation
- Impaired balance and hand-eye coordination
- Excessive sweating
- Increased salivation
- Drowsiness
- Fatigue
- Motion sickness

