All pediatric patients (ages 13-18) undergoing corrective scoliosis surgery at Connecticut Children's over a span of 12 months (03/01/24-03/01/25) will be approached by a study team member during the pre-operative stage with information and consent documentation about the study. If the patient acknowledges that they are interested and would like more information, then the study team member will complete the formal consent and HIPAA process with the patient and family. This will take place in a private setting, and the patient/family will be given ample time to read the consent and have any questions answered. As a part of the consent and HIPAA, patients will consent to the study procedures as well as the research study team accessing their medical record for data collection. Each patient's MRN will be entered into a secure password protected Excel enrollment log and be given a subject identification number for de-identification. During the consenting procedure, the patient will utilize the VR device for 5 minutes to screen for side effects and become accommodated to the device. In the event that the patient experiences side effects during this 5-minute period, they will be excluded from the study.

Retrospective chart review sample:

The retrospective chart review is intended to be used as a historical control to the prospective arm of the study. All patients in the retrospective time frame (02/01/19 - 02/01/24) will be identified using CPT codes (fusion codes: 22800, 22802, 22804 and instrumentation codes: 22842, 22843, 22844) as well as ICD-10 Code M41.* from Slicer Dicer. These patient's charts will be verified by a study team member to ensure they meet inclusion criteria, and then they will be entered into a using a secure password protected Excel enrollment log. Each patient's MRN will be recorded into the enrollment log and will be given a subject identification number for de-identification. Patients in this cohort will not be approached for consent as we will not collect identifiable information and only their deidentified medical record will be in review. It is also likely that some patients are no longer clinically active at Connecticut Children's, and therefore we would not be able to contact these patients for consent.

Study Retention/Withdrawal

Prospective Cohort:

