
Retrospective Arm:

Eligible patients verified for the retrospective chart review will be entered into a secure Excel enrollment log and be deidentified by using a subject identification number. The MRN and subject ID will be entered into a linking file that will be password protected and only accessible to authorized study personnel. The following information will be collected from the patient charts: demographics, degree of scoliosis, surgical details, PT notes, pain medication regimens, associated pain scales, and relevant follow up notes. These data will be entered into REDCap in a de-identified manner and will only be accessible to authorized study team members.

Sample Size Justification

This study will utilize a convenience sample of patients presenting to Connecticut Children's for a scoliosis surgery within the study timeframe.

Feasibility, Accrual, and Duration of Accrual

Accrual will occur over a 12 month period (03/01/24 - 03/01/25). Approximately 60-80 patients undergo a surgical procedure for the correction of scoliosis annually at Connecticut Children's. We estimate ~40% will decline to participate, therefore we anticipate approximately 35-50 patients being included in the prospective arm of study. For the retrospective arm of the study, we approximate to include 350 patients for chart review.

Study Limitations

This study is limited in that we are only assessing the utility of VR to reduce pain in a specific patient population (pediatric patients undergoing surgical correction of scoliosis), at a specific time (the immediate post-operative period), at a single institution (Connecticut Children's), and within a relatively small sample size, which limits the generalizability of the study to apply to other patient populations. This study is also limited in that it utilizes a retrospective chart review as a historical control. By collecting data retrospectively, it is likely that the study team will encounter missing variables and will not be able to categorize pain as accurately as they would be able to in a prospective or true randomized control trial study designs.

Data Analysis

- Intention to treat analysis
- A biostatistician will assist in analysis
- Descriptive statistics (frequency, percentage, mean, standard deviation, median, and interquartile range) will be utilized to describe the two groups (VR and control)

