- Fisher's Exact test, independent t-tests, and Wilcoxon Rank Sum tests will be used for univariate analysis to compare demographics between the two groups (VR and control)
- Pain outcome:
 - Univariate analysis using independent t-tests or Wilcoxon rank sum tests will be used to compare the daily mean pain scales
- Opioid utilization outcome
 - Univariate analysis using independent t-tests or Wilcoxon rank sum tests will be used to compare the total inpatient dose of opioids administered

Administrative Organization/Roles and Responsibilities

- Principal Investigator - [name] - Connecticut Children's Division of Neurosurgery
- Co-Principal Investigator – [name] – UConn Department of Psychological Sciences
- Co-Principal Investigator – [name] – Connecticut Children's Division of Orthopedic Surgery
- Co-Principal Investigator – [name] MPH – Connecticut Children's Division of Pain and Palliative Medicine
- Student Coordinators and Responsibilities:
 - [name] – Study Coordinator
 - Study Design

- Data quality
- Data analysis
- Project management
- Manuscript drafting
- [name] – Medical student
 - Study design
 - Study Procedures
 - Data analysis
 - Manuscript drafting
- [name] – Medical Student
 - Study Design
 - Study procedures
 - Data analysis
 - Manuscript drafting

Use of Study Results

The data generated from this study will be used to re-evaluate the postoperative pain management pathway for pediatric patients in the post-operative period following spinal deformity surgery. These data will also be used for presentations / publications.

Study Budget

Item	Quantity	Per
VR Computer	1	\$3,100
VIVE Wireless Head Mounted Display	1	\$1,100
Cleanbox	1	\$2,000
Computer supplies (external hard drives, batteries, sanitizer wipes)	1	\$200
VR Software	1	\$500
TOTAL		\$6,900

References:

1. Janicki, J.A. and B. Alman, *Scoliosis: Review of diagnosis and treatment*. Paediatr Child Health, 2007. **12**(9): p. 771-6.

2. Al-Mohrej, O.A., S.S. Aldakhil, M.A. Al-Rabiah, and A.M. Al-Rabiah, *Surgical treatment of adolescent idiopathic scoliosis: Complications*. Ann Med Surg (Lond), 2020. **52**: p. 19-23.
3. Sung, S., et al., *Incidence and Surgery Rate of Idiopathic Scoliosis: A Nationwide Database Study*. Int J Environ Res Public Health, 2021. **18**(15).

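### Pain and opioid outcomes are compared with historical controls by unadjusted tests only, so case mix, selection or practice change could mimic or hide a VR effect

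*Combined protocol and SAP*

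**What the plan says.** Study Procedures explains that a randomised trial is not feasible and that VR patients will be compared with a chart-review historical control. Data Analysis specifies two outcome comparisons. For pain: "Univariate analysis using independent t-tests or Wilcoxon rank sum tests will be used to compare the daily mean pain scales". For opioids: "Univariate analysis using independent t-tests or Wilcoxon rank sum tests will be used to compare the total inpatient dose of opioids administered". Baseline differences are handled only by significance tests on demographics, and no consequence is attached to the result. Regression, matching, weighting, stratification and calendar terms are all absent.

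The material for adjustment is collected. For the retrospective arm: "The following information will be collected from the patient charts: demographics, degree of scoliosis, surgical details". The prospective arm has the same items, and the list of collected data defines surgical details to include the number "of spinal levels involved in fusion" and the duration of surgery.

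Entry to the two arms differs. In the feasibility section: "We estimate ~40% will decline to participate". The recruitment section adds a 5-minute VR trial: "In the event that the patient experiences side effects during this 5-minute period, they will be excluded from the study". Controls are checked against the inclusion criteria but face neither filter.

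Study Limitations names the historical control, warns that "it is likely that the study team will encounter missing variables", and expects less accurate pain data. It does not mention confounding or change in practice.

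**The concern.** Without randomisation, an unadjusted test estimates the VR effect plus every other difference between the arms. Three sources are built into this design:

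- **Case mix:** for example, levels fused or curve severity.
- **Selection:** VR patients must agree to take part and tolerate the device.
- **Calendar time:** the arms share none.

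The first can be reduced with data the study already collects, and the plan does not do so. Any of the three can act in either direction, producing an apparent benefit or concealing a real one. Under Use of Study Results, the findings are meant to inform a re-evaluation of the postoperative pain pathway, so attribution to VR matters.

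**Working it through.** **Inputs from the documents.** 60-80 operations a year, about 40% declining, 35-50 VR patients, about 350 controls, a hypothesised pain difference of at least 1 point, and the accrual windows.

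**Inputs assumed.** Two-sided alpha 0.05; pain SD 1.5-2.5 points; all imbalances, correlations and drifts. The documents give none of these.

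**The plan's own figures.** 60 × 0.6 = 36 and 80 × 0.6 = 48, against a stated 35-50. 5 years × 70 = 350, as stated. The counts reproduce.

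**Calendar gap.** The control window 03/01/19-03/01/24 has its midpoint at 30 August 2021. The VR window 03/01/24-03/01/25 has its midpoint at 30 August 2024. The gap is 3.00 years, or 3.08 with the other control window the protocol gives. This is an average gap: the control window is 5 years long and the whole span about 6.

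**Formulas.** SE = SD × √(1/n + 1/350). Probability of rejection with a net difference b: Φ(b/SE − 1.96) + Φ(−b/SE − 1.96). In SD units, √(1/n + 1/350) is 0.177, 0.163 and 0.151 for n = 35, 42 and 50. In points, SE runs from 0.227 (SD 1.5, n = 50) to 0.443 (SD 2.5, n = 35), and is 0.327 at SD 2, n = 42.

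**(a) Case mix, no VR effect.** Bias in SD units = imbalance × correlation with the outcome.

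| Imbalance | Correlation | Bias (SD) | Bias (points, SD 1.5-2.5) | False positives, n = 35-50 |
|---|---|---|---|---|
| 0.3 SD | 0.3-0.5 | 0.09-0.15 | 0.14-0.38 | 8.0-16.8% |
| 0.5 SD | 0.3-0.5 | 0.15-0.25 | 0.23-0.63 | 13.5-38.0% |

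Simulation at 42 versus 350 (4,000 runs per setting) gave unadjusted rates of 8.5%, 14.5%, 15.6% and 33.3% for (imbalance, correlation) = (0.3, 0.3), (0.3, 0.5), (0.5, 0.3) and (0.5, 0.5). Adjusting for the covariate gave 4.3-5.5%.

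**(b) Any net non-VR difference, whatever its source.**

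| Net difference | False positives, no VR effect | Power for a true 1-point benefit if opposed, SD 2, n = 42 | Same, full ranges |
|---|---|---|---|
| 0 | 5% | 86.5% | 62-99% |
| 0.3 point | 10-26% | 57% | 35-87% |
| 0.6 point | 27-75% | 23% | 15-42% |

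**(c) Baseline tests as a safeguard.** A true 0.3 SD imbalance is flagged with probability 39.5%, 45.1% and 51.0% at n = 35, 42 and 50. At 0.5 SD it is 81-91%. The plan applies these tests to demographics only, so levels fused and surgery duration are not tested at all.

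**The case against.** The strongest objection is that the size of the harm is assumed throughout. The documents do not show that practice at this site changed between 2019 and 2025. The Background says that "patients undergo multimodal pain management following scoliosis correction" but gives no adoption date. The return to about 5% after adjustment holds by construction, for one fully observed linear covariate. This stands: the figures show sensitivity, not expected bias.

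Second, p < 0.05 is not the only possible yardstick. The pain hypothesis is a difference of at least 1 point. Judged by whether the observed difference reaches 1 point, a spurious 0.6 point would do so about 11% of the time at SD 2, n = 42 (4-18% over the ranges), and 0.3 point about 2% (0.1-6%). This is a fair tempering. However, the plan states 1 point as a hypothesis, not a decision rule; the analyses it specifies are significance tests; and the estimate is biased under either yardstick.

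Third, baseline tests would usually flag a 0.5 SD imbalance. That is true of the variables tested, but detection corrects nothing when no action follows.

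Fourth, one site, idiopathic scoliosis only and ages 13-18 already narrow case mix, and the plan openly lists the historical control as a limitation. Both deserve credit. Neither addresses severity, selection or time, and the stated limitation concerns data quality, not confounding.

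Finally, adjustment cannot repair everything. Pain in the VR arm is recorded around VR and PT sessions, while control pain comes from charts. VR patients who withdraw, or decline three consecutive sessions, are left out of the analyses. These belong in the caveats.

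**Conclusion.** The concern holds and should be fixed before analysis. Followed exactly, the plan yields unadjusted estimates for its primary outcome and a key secondary outcome from non-randomised arms, while leaving relevant covariates it collects unused. That conclusion rests on the text alone and does not require proof that local practice changed. The numerical size rests on the assumed alpha, SD, imbalances, correlations and drifts. Within those ranges, modest differences are enough to raise the false-positive rate well above 5% or to remove most of the power for 1 point. All point-scale figures are for pain; no opioid illustration was possible from the documents. Neither the size nor the direction of any actual bias is established.

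**What to change.** 1. **Primary analysis.** Pre-specify a regression for each outcome: linear for the plan's daily mean pain (stating whether it is per day, repeated-measures or averaged over the stay) and log-scale for total opioid dose. Adjust for age, sex, levels fused, surgery duration and degree of scoliosis. Blood loss could be added; it is left out only to keep the model small. Keep the unadjusted tests as supportive, and state how missing covariates are handled. Propensity overlap weighting is an alternative, but it targets a different population.
2. **What adjustment leaves.** State that it does not remove calendar drift, selection by refusal and VR screening, differences in pain-measurement timing, or the exclusion of withdrawn patients. Name confounding and practice change in Study Limitations. Add a sensitivity analysis using the surgery-date trend within controls, recent controls only, or both.
3. **Control window.** Inclusion/Exclusion Criteria gives 03/01/19-03/01/24 and the retrospective sampling section gives 02/01/19-02/01/24. State one window, ending before VR enrolment opens.

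**Cost.** SAP wording and modest analysis, with no new patients or chart review. Surgery date is not a listed data item, but it must be known to apply the control window; it would need to reach the analysis file in a form compatible with de-identification. The adjusted result may be less favourable to VR.

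The sensitivity analyses lose precision. With uniform accrual, a linear time term adds 3²/(350 × 25/12 + n/12) to (1/n + 1/350), inflating variance 1.39, 1.46 and 1.54 fold at n = 35, 42 and 50. Power for 1 point at SD 2 falls from 80-91% to 67-76%. It also extrapolates, because the arms share no calendar time, and it cannot separate VR from an abrupt change when enrolment opens. Restricting to the last 2 control years (350/5 × 2 = 140 patients, if accrual was even) halves the midpoint gap to 1.5 years, with 75-86% power. Residual confounding remains under every option.

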Appendix A – Data Collection Tool

Appendix B – FACES pain scales
